oxide-eugenol (Kerr Corporation, Orange, CA, USA). After the root canal treatment is done, the patient will be treated by [name], a general dentist for the restorative aspect of the procedure. Depending on how much tooth structure is left, he will decide which kind of build-up material to use and if a post is needed. The tooth will be restored with a crown for posterior teeth, or a composite filling for anterior teeth.

The goal is to follow-up all treated teeth 6 months and 1 year post-RCT. Appointment letters will be mailed to the patients 1 month prior to the follow-up dates. Patients, who failed to attend for recall, will be contacted with a personal courtesy call by the study team member (dentist on study team) and a more detailed explanation letter will be mailed to encourage them to attend follow-up appointments. If patients continue to not attend for recall, then the reasons provided by each patient (if provided) will be recorded. Recall appointments can be made as necessary other than the 6-month and 1-year follow-up appointments. Recall appointments will have their own specific form detailing the patient's reason and required procedure. Possible complications will be communicated to the patient prior to the study and will be dealt with on a case by case basis.

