Follow-up examination consists of updating the general and endodontic history of the treated teeth upon clinical and radiographic examination. All patients will be interviewed and examined by one individual from the study team to remain consistent and reduce sources of bias from involving multiple individuals. Extraoral examination will be performed, which includes palpation of masticatory, neck and shoulder muscles, lymph nodes, and palpation of the temporomandibular joint for tenderness or any abnormalities. Clinical examination of the treated teeth will be carefully noted in detail, including the following details: (1) tenderness to percussion of the tooth, (2) tenderness to palpation of adjacent soft tissues, (3) presence of sinus tract or abscess, (4) periodontal probing depths around the tooth, (5) type/presence of coronal seal and restoration. Further examination of the restoration will be done and classified into the following three categories: (A) visual or tactile exposure of root filling material, (B) clinical or radiographically detected marginal discrepancy but without visual or tactile exposure of root filling to the oral cavity, (C) satisfactory coronal restoration with good retention and margins.

The radiographs will be taken digitally with size 1 or 2 XDR Digital Intraoral sensors (XDR Radiology, Los Angeles, CA, USA). The images will then be transmitted and analyzed by the XDR program.

If the patient feels persistent discomfort from the treated tooth at follow-up, periapical radiographs at different horizontal angles will be taken to detect any radiolucent pathology that may be superimposed upon the root. If the patient is pregnant at the time of the follow-up appointment, the radiographic examination will be deferred until after delivery.

All the preoperative, immediate post-obturation, and follow-up radiographs will be viewed on the computer screen with the "caries" and "endo" detection feature and magnifying viewer tools in the XDR program as needed. The preoperative periapical status of each root will be classified into three categories: (1) intact periodontal ligament, (2) widened periodontal ligament or (3) periapical lesion. The diameter of the lesion preoperatively and at follow-up was measured using the measuring ruler tool in the XDR program. The diameter for widened periodontal ligament will be recorded as

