0.5 mm. The quality of previous treatment will be judged satisfactory if a well-condensed root filling extends to within 2 mm of the radiographic root apex.

Treatment success will be evaluated based on two outcome measurements: (1) absence of apical periodontitis via clinical and radiographic evaluation, (2) tooth survival.

The assessment of treatment success will strictly be defined as absence of pain, clinical signs of inflammation or swelling, and radiographic measures of complete healing (i.e. presence of normal periodontal ligament space, intact lamina dura, etc). A potential consideration for treatment success will also include aspects from the patient such as the absence of pain and/or clinical signs of inflammation or swelling and radiographic measures of complete healing or *incomplete healing* (i.e. reduced size of periapical lesion without normal periodontal ligament space width).

In some of these cases where the failure is not due to an iatrogenic perforation, a secondary RCT, also called non-surgical endodontic retreatment, might be indicated to resolve any pulp tissue that may have been left behind. A secondary RCT may also be necessary if there is failure of primary RCT due to narrow or curved canals were not treated during the initial procedure, complicated canal anatomy went undetected in the first procedure, placement of the crown or other restoration was delayed following the endodontic treatment, inadequate seal during primary RCT and a radiolucency that still persists or expands. Furthermore, a secondary RCT is indicated if any infection from primary RCT causing persistent pain and or periapical lesion seen in the radiograph. This secondary RCT will still be done with NDGP in the middle third of the root, as the cause of failure in the first place would have been because of regular in-tact gutta percha extruding from the apex or insufficient instrumentation.

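### Tooth survival is an outcome, but for a patient who attends no later visit the plan records only the reason for absence, although a study dentist already telephones non-attenders and could ask about the tooth

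*Combined protocol and SAP*

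**What the plan says.** All of this is in the Study Protocol section unless noted.

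- **Outcomes.** "Treatment success will be evaluated based on two outcome measurements: (1) absence of apical periodontitis via clinical and radiographic evaluation, (2) tooth survival". Only the first is tied to an examination.
- **Schedule.** "The goal is to follow-up all treated teeth 6 months and 1 year post-RCT".
- **Source of data.** Tooth status is obtained when the patient attends: "Follow-up examination consists of updating the general and endodontic history of the treated teeth upon clinical and radiographic examination".
- **Contact with non-attenders.** A patient who misses recall "will be contacted with a personal courtesy call by the study team member (dentist on study team"). The patient is also sent a letter whose stated purpose is to bring about attendance, not to collect outcomes.
- **Data on continuing non-attenders.** One item is named for those who still stay away: "If patients continue to not attend for recall, then the reasons provided by each patient (if provided) will be recorded".
- **Exclusions.** The paragraph on recruitment and eligibility lists teeth to be left out of the periapical-status analysis: those followed for less than 6 months, those extracted for non-endodontic reasons, and those with no periapical information at extraction. The paragraph on risks and extractions counts an extraction for endodontic problems as a failure. It also removes extractions that lack periapical information after treatment, but does not say from which analysis.

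No part of the document obtains tooth status by telephone, from the patient's own dentist or from dental records. The Statistical Analysis section covers only the mechanical properties of the filler, so it gives no missing-data rule for survival.

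**The concern.** The periapical outcome needs a clinical and radiographic examination. Tooth survival does not: a patient can say whether the tooth is still there. The plan already provides the caller, the call and the list of patients to be called, but specifies no question about the tooth. For someone who never returns, the only specified datum is a reason for absence, and even that depends on the patient offering one.

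Two things are at stake. The first is loss of information on one of two named outcomes in arms of 15, where each patient is a large fraction of the arm. The second is possible bias. A patient whose tooth was extracted elsewhere has little reason to come back to have it examined, so absence may be related to the outcome. The Summary's rationale for the new filler is that it may prevent fracture and reduce the need for extraction, so an unseen extraction would be a missed event of direct interest.

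**Working it through.** **Inputs.** Arm size n = 15 (Summary). Number per arm with unknown survival status, m: not in the documents, so 1 to 5 is assumed. The 15 per arm comes with no power, margin or dropout rate, so there is no plan figure to reproduce, and the check does not depend on one.

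**Between-arm difference.** Let s1 and s0 be the teeth known to be present in the two arms. With m unknown in each arm, true survival in an arm lies between s/15 and (s + m)/15. The difference therefore lies within (s1 − s0)/15 ± m/15.

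| Unknown per arm (assumed) | m/15, percentage points each way |
|---|---|
| 1 | ±6.7 |
| 2 | ±13.3 |
| 3 | ±20.0 |
| 4 | ±26.7 |
| 5 | ±33.3 |

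Each patient whose status is learned removes 1/15 = 6.7 points from the range for that patient's arm.

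**One arm, 3 patients unseen (assumed), all 12 seen having the tooth.**

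- No calls answered: survival lies between 12/15 = 80% and 15/15 = 100%. The lower end requires all three to have lost the tooth.
- Two of the three reached, both teeth present: 14/15 = 93.3% to 15/15 = 100%.
- Two reached, one tooth extracted: among those with known status, survival is 13/14 = 92.9%, against 12/12 = 100% from attenders alone.

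**Precision.** If every observed tooth survives, the exact two-sided 95% lower limit is 0.025^(1/n): 73.5% with 12 teeth and 78.2% with 15.

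**Interaction with the extraction exclusion.** An extraction learned of by telephone will usually come without periapical information. If the unqualified exclusion is applied to survival, that tooth leaves the analysis while teeth reported as present stay in. In the third case above, 13/14 = 92.9% becomes 13/13 = 100%. If all three are reached and one tooth was extracted, 14/15 = 93.3% (exact 95% interval 68.1% to 99.8%) becomes 14/14 = 100%. Adding the questions without changing that rule could build in an upward bias.

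**The case against.** The strongest reply is that the gap is narrower than it looks. Four parts of that reply stand.

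- A reader might infer that the call itself is used to record only the reason for absence. The text does not say so. It describes the call and letter as a means of encouraging attendance and, separately, the recording of reasons if absence continues.
- A reader might infer that any missed visit loses the survival outcome. It does not. Someone absent at 6 months but seen at 1 year still supplies it. Recall appointments at other times are allowed, each with its own form, and persistent pain or an extraction may bring a patient to the team's attention. The loss concerns patients who attend no later visit.
- A patient may give the extraction as the reason for not attending, and that would be written down. This helps, but it depends on the patient volunteering it and is not a structured outcome record.
- A reader might conclude that survival is certain to be biased upward because those lost are the ones who lost teeth. The documents contain no evidence on that. It is plausible, not shown.

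It can also be said that this is a 30-patient pilot in which survival has no stated definition or time point and no clinical outcome has an analysis. Those gaps weigh more. They do not remove this one, which can be closed at little cost.

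**Conclusion.** The point holds in this form: for a patient who attends no later visit, the plan specifies no means of learning whether the tooth survived, although it already plans a contact that could supply the answer. The loss of information does not depend on why patients stay away. Each patient per arm without status adds 6.7 points in each direction to the undetermined part of the survival difference, which is ±20 points at three per arm. The number missing is an assumption throughout, because no dropout rate is given. Upward bias is conditional on non-attendance being linked to tooth loss.

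No figure in the plan is contradicted. The 86% success rate quoted for primary root canal treatment is not a tooth-survival rate and has not been used as one. This is a worthwhile, low-cost improvement to data collection; it does not show that the trial's survival result will be wrong.

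**What to change.** 1. **Recall paragraph.** Have the dentist who makes the courtesy call ask and record, in the same words in both arms, whether the treated tooth is still present and, if not, the date of and reason for its extraction. Record the date of the call. Presence alone gives survival status; the reason is needed because the plan distinguishes extraction for endodontic problems from other extractions.
2. **Survival outcome.** Use these answers for survival, marked as patient-reported. Report by arm how many patients' status stays unknown, with best-case and worst-case bounds over all 15.
3. **Paragraph on risks and extractions.** Limit the exclusion of extractions without periapical information to the periapical-status analysis, as the recruitment and eligibility paragraph already does, so that extractions reported by telephone count in survival.

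**Cost.** Up to three questions on a call already planned, one line on the form and one qualifying phrase in the text. The downside is that survival for these patients is self-reported. Patients who cannot be reached remain unknown, and the periapical outcome still needs the visit.

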
## **Study Protocol:**

[name] will recruit the patient for this study after the patient's referral to the UCLA endodontics department for root canal therapy. Informed consent will be obtained by [name] from all the patients that will be able to be taken home for patients to consider being part of this pilot study. We will stress to the patient that there will be an intended benefit and that we will be providing an incentive for joining this study (parking vouchers). The sample population will be screened and collected [name], M.S.,

Ph.D., D.D.S. All of the patients must be over 18 years of age when the treatment commences. Teeth will be excluded from this study if they had preoperative periodontal disease, prior non-surgical and surgical endodontic treatment, or if the apex/apices under investigation is/are not discernible in any of the periapical radiographs. The teeth that will be excluded from the analysis of the 'periapical status following treatment' are if: (1) they were not followed-up for at least 6 months, (2) if they were extracted for reasons not related to endodontic problems (for e.g. periodontal disease), (3) information on the periapical status during the time of extraction was not available.

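### Teeth without 6 months of follow-up leave the periapical analysis, and nothing in the plan shows how far they could move the result

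*Combined protocol and SAP*

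**What the plan says.** The Study Protocol section lists three grounds for leaving a tooth out: "The teeth that will be excluded from the analysis of the 'periapical status following treatment' are if", the first being that "they were not followed-up for at least 6 months". No visit window or tolerance is attached to that minimum.

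The follow-up paragraph of the same section sets the schedule: "The goal is to follow-up all treated teeth 6 months and 1 year post-RCT". Other visits are possible: "Recall appointments can be made as necessary other than the 6-month and 1-year follow-up appointments". The Summary adds that extra visits before the 6-month and 1-year appointments may be needed for infection or persistent pain.

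There is a real effort to limit loss. "Appointment letters will be mailed to the patients 1 month prior to the follow-up dates", and patients who miss a recall "will be contacted with a personal courtesy call by the study team member" and are sent a fuller letter. After that the plan says: "If patients continue to not attend for recall, then the reasons provided by each patient (if provided) will be recorded".

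The Statistical Analysis section describes a t test on mechanical properties of the material. The documents contain no clinical analysis method, imputation, best-case or worst-case bound, or other sensitivity analysis for missing outcomes.

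**The concern.** Absence of apical periodontitis is the first of the two success measures, and the Summary's hypothesis is that NDGP does not worsen clinical outcome. For a claim of that kind, removing unknown or early outcomes can produce reassurance that the data do not support.

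Two kinds of tooth are affected. The first has no reading at all. The second was examined, but only before 6 months: at an unscheduled visit for infection or pain, or at a visit that fell slightly early and was not followed by another. Teeth seen only because of symptoms are more likely to be failures. Dropping them raises the reported success rates, and if there are more of them in the NDGP arm it hides a difference.

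The arms are small enough for this to matter. The Study Protocol section cites about 86% success for primary treatment, which implies about two failures in 15. Three excluded patients in an arm would outnumber the expected failures.

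**Working it through.** The plan gives no figure to reproduce: 30 patients are stated without power, margin or expected loss.

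**Inputs**
- 15 patients per arm (Summary). One tooth per patient is assumed.
- Background success of about 86% (Study Protocol section), cited there as context and not as a design value. Expected successes are 15 × 0.86 = 12.9, so about 2.1 failures.
- m = patients excluded per arm. The documents give no loss rate, so m = 1 to 5 (7% to 33%) is assumed.

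**Extreme-case bounds.** Let s be the observed successes among 15 − m, chosen near 86%. Counting every excluded patient as a failure gives s/15. Counting every one as a success gives (s + m)/15. With equal s and m in both arms the observed difference is 0, and the sample difference lies between s/15 − (s + m)/15 = −m/15 and +m/15.

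| m per arm | Observed | Arm range over 15 | Range of difference |
|---|---|---|---|
| 1 | 12/14 = 85.7% | 80.0% to 86.7% | ±6.7 points |
| 2 | 11/13 = 84.6% | 73.3% to 86.7% | ±13.3 points |
| 3 | 10/12 = 83.3% | 66.7% to 86.7% | ±20.0 points |
| 4 | 9/11 = 81.8% | 60.0% to 86.7% | ±26.7 points |
| 5 | 9/10 = 90.0% | 60.0% to 93.3% | ±33.3 points |

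**Loss in one arm only.** Take GP complete at 13/15 (86.7%) and NDGP at 10/12 with 3 excluded. The observed difference is 83.3 − 86.7 = −3.3 points (from unrounded rates). The bounds are 10/15 − 13/15 = −20 points and 13/15 − 13/15 = 0.

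**Early visits.** A tooth seen early is lost only if no later visit follows. Expected exclusions are 30 × P(early) × P(no later visit), with both probabilities assumed. At 25% and 20% this is 30 × 0.25 × 0.20 = 1.5 patients. Over 10% to 50% early and 10% to 30% not returning, it runs from 30 × 0.10 × 0.10 = 0.3 to 30 × 0.50 × 0.30 = 4.5.

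**Extractions.** The Study Protocol section counts extraction for endodontic problems as a failed outcome, with no minimum time. The 6-month rule, read literally, would exclude such a tooth if it was extracted earlier. The two statements need to be reconciled.

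**The case against.** The strongest reply has five parts.

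1. *Early attenders.* A reader might infer that everyone seen slightly before 6 months is lost, or that the cut-off is an exact calendar date. The documents do not support either. The rule is a minimum on total follow-up, so a 1-year visit or any later recall brings the tooth back. The strict-date reading is only an inference from the missing window; a nominal-visit reading is also natural. This stands, and it makes early attendance a minor part of the point.
2. *The bounds are extreme.* A reader might take ±20 points as the range of the true treatment difference. It is the range of the difference in these 30 patients. It requires all three excluded patients in one arm to fail and all three in the other to succeed. If absence were unrelated to outcome and success were 10/12, that has probability (10/12)³ × (2/12)³ ≈ 0.3% in each direction. Sampling error at 10/12 versus 10/12 is larger: 1.96 × √(2 × 0.833 × 0.167 / 12) ≈ ±30 points. This stands as a limit on interpretation. The bounds still show what exclusion alone could do, without assuming why patients were absent.
3. *No margin.* The plan states no margin or decision rule, so the bounds cannot be passed or failed. This stands.
4. *A larger gap comes first.* No clinical analysis is specified at all, so it goes too far to say that the plan assumes absence is unrelated to outcome. That is fair. The exclusion rule is nevertheless explicit, and its effect can be shown whichever analysis is chosen.
5. *Retention effort and scope.* Letters and a call may keep losses low, and the rule is not expressly applied to tooth survival. Both are true. Neither says what to do with losses that still occur in the periapical analysis.

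**Conclusion.** The point holds in a limited form. The plan has an explicit exclusion rule for the periapical outcome and nothing that shows how far the excluded teeth could change the result. Because unscheduled visits for infection or pain can precede 6 months, the rule can remove symptomatic teeth, so exclusion need not be unrelated to outcome.

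Each excluded patient is worth 6.7 points of an arm. With equal observed rates and m excluded per arm, the extreme-case range for the sample difference is ±m/15, or about ±7, ±20 and ±27 points for 1, 3 and 4. These sizes rest on assumed losses and one tooth per patient. The early-visit count of 0.3 to 4.5 patients rests wholly on assumption and should not carry the argument. For a pilot this is an inexpensive improvement that should be made; it does not invalidate the design.

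**What to change.** 1. Keep the existing minimum, so that a tooth first seen at 8 months or 1 year, or one whose radiograph was deferred for pregnancy, still qualifies. Add a small stated tolerance before 6 months. Do not replace the rule with attendance at the 6-month visit, which read literally would exclude those later readings.
2. Report the number excluded in each arm, with reasons and last known clinical status.
3. Beside the observed-case success rates, add one supporting table on all 15 randomised per arm. Use any failure observed before 6 months, and give both extremes for patients without a usable reading: unseen NDGP as failures with unseen GP as successes, and the reverse.
4. Reconcile the 6-month rule with the statement that endodontic extraction is a failed outcome.
5. Present the bounds as a sensitivity range that qualifies any statement that NDGP does no harm to outcome, not as a pass/fail test.

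The cost is a few sentences and one table, with no extra patients or visits. The downside is a wider and less favourable stated range.

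### The rules for classifying treatment success conflict for some extracted teeth and leave the deciding visit, the looser definition and retreated teeth open, so the result can depend on choices made after the data

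*Combined protocol and SAP*

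**What the plan says.** All the relevant text is in the Study Protocol section unless stated otherwise.

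- **Outcomes.** "Treatment success will be evaluated based on two outcome measurements": absence of apical periodontitis on clinical and radiographic evaluation, and tooth survival. Neither has a time point or a rank.
- **Strict definition.** "The assessment of treatment success will strictly be defined as absence of pain, clinical signs of inflammation or swelling, and radiographic measures of complete healing". No visit is named.
- **Looser version.** The next sentence begins "A potential consideration for treatment success will also include aspects from the patient such as the absence of pain and/or clinical signs" and goes on to accept incomplete as well as complete radiographic healing. It is not called secondary, sensitivity or exploratory.
- **Visits.** "The goal is to follow-up all treated teeth 6 months and 1 year post-RCT". In addition, "Recall appointments can be made as necessary other than the 6-month and 1-year follow-up appointments", and for a patient who is pregnant at follow-up "the radiographic examination will be deferred until after delivery".
- **Retreatment.** Among other indications, "a secondary RCT is indicated if any infection from primary RCT causing persistent pain and or periapical lesion seen in the radiograph". The paragraph speaks of failure of the primary root canal treatment (RCT) but does not say how a retreated tooth is scored at a later visit.
- **Extraction.** The paragraph on risks and extractions classes extraction for endodontic problems (persistent pain, swelling, sinus or periapical lesion) as a failed outcome. Its next sentence removes from analysis every extraction that lacks postoperative periapical information. The opening paragraph has a similar exclusion, limited to the analysis of periapical status, and a minimum follow-up of 6 months.
- **Statistics.** The Statistical Analysis section covers laboratory properties of the material only.

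**The concern.** The clinical hypothesis in the Summary is that NDGP has no negative effect on outcome compared with GP. No margin or clinical test is given. A claim of that kind is helped by anything that hides failures, or that allows the kinder of several readings to be reported.

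Three features allow this. One stated rule counts an extracted tooth as a failure while another drops the same tooth. A second version of success stands beside the strict one without a role. Finally, the text does not say which visit decides, or whether a tooth that failed and was retreated still counts as a failure later. In arms of 15, moving one or two teeth changes the picture.

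**Working it through.** **Inputs from the documents:** 15 patients per arm (Summary), and a success rate of about 86% for primary RCT (risks and extractions paragraph, with no visit or definition attached).

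**Assumptions:** one tooth per patient, no loss before analysis, GP at 86% and NDGP at 71% (a 15-point deficit) at both visits, and between-visit correlation ρ of 0.6 to 0.9 on a latent normal scale. The yardstick is the NDGP rate being at least as good as the GP rate. The plan gives no clinical figure to reproduce.

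**Step 1: the extraction rules side by side.** Take a tooth extracted for persistent pain with no periapical information. The reason makes it a failure; the missing information excludes it. The text gives no precedence.

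**Step 2: size of one tooth.** 1/15 = 6.7 points. Example: GP 13/15 = 86.7% and NDGP 11/15 = 73.3%, a deficit of 13.3 points.
- If one extracted NDGP tooth is dropped: 11/14 = 78.6%, deficit 8.1.
- If one retreated NDGP tooth is read as a success: 12/15 = 80.0%, deficit 6.7.

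**Step 3: dropping failures in both arms.** If a fraction f of failures is dropped, the apparent rate is p / [p + (1 − p)(1 − f)].

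| f | GP | NDGP | Deficit |
|---|---|---|---|
| 0.10 | 0.86/0.986 = 87.2% | 0.71/0.971 = 73.1% | 14.1 |
| 0.25 | 0.86/0.965 = 89.1% | 0.71/0.9275 = 76.5% | 12.6 |
| 0.50 | 0.86/0.930 = 92.5% | 0.71/0.855 = 83.0% | 9.4 |

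By simulation, the chance that NDGP looks strictly better rises from 0.105 to 0.13, 0.15 and 0.18. The chance of equal or better moves less (0.213 to about 0.20, 0.20 and 0.24), because unequal denominators break ties. The shrinkage of the deficit is systematic.

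**Step 4: one fixed visit.** With X ~ Bin(15, 0.86) for GP and Y ~ Bin(15, 0.71) for NDGP, exact summation gives P(Y ≥ X) = 0.213 and P(Y > X) = 0.105. About half of the 21% is ties.

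**Step 5: either visit may be chosen** (200,000 simulated trials per setting).

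| True deficit | Equal or better, one fixed visit | Equal or better, either visit (ρ 0.9 to 0.6) |
|---|---|---|
| 10 points | 32% | 43–48% |
| 15 points | 21% | 30–34% |
| 20 points | 13% | 20–23% |

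At 15 points, NDGP is strictly better in 10.5% of trials at a fixed visit and 16–18% at either.

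**Step 6: the looser definition at one visit.** If it passes 1, 2 or 4 points more teeth than the strict one, and either may be reported, 21% becomes 23, 24 or 25%. This is smaller than the visit effect.

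**Step 7: retreatment.** If 10, 25 or 50% of failures in both arms are retreated and then read as successes, the deficit is 15 × (1 − share) = 13.5, 11.3 or 7.5 points.

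**The case against.** **The definitions are already ranked.** 'Strictly' governs the first version, and the second is only a potential consideration. This largely stands. Lesions of reduced size should also be uncommon, because the endodontic exclusions bar periapical radiolucency, although the size cut-off is left open. A reader might infer that the looser version is a wide loophole, since its 'and/or' taken literally could pass a painful tooth. The documents do not support that as the intention: extraction for persistent pain is a failure elsewhere. What remains is a missing label and a loose conjunction.

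**Retreated teeth are already called failures of the primary RCT.** This is true of the wording, so one cannot say that the plan counts them as successes. Only the scoring rule at a later visit is missing.

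**The extraction conflict is narrow.** The opening paragraph limits its exclusion to the periapical analysis, and survival is a separate outcome. That stands for the opening paragraph. The exclusion in the extraction paragraph has no such limit and directly follows the failure rule.

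**A pilot may simply tabulate both visits.** It may, but the plan does not say so, and tabulation does not settle which visit supports the conclusion. A reader might also take the 6-month minimum as naming the visit. It is only an eligibility floor.

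**The figures rest on assumptions.** They do. Only the 86% and the 15 per arm come from the documents.

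**Conclusion.** The point holds in this form: two stated rules conflict for teeth extracted for pain or swelling without periapical information, and the deciding visit, the role of the looser version and the later scoring of retreated teeth are left open. One tooth is 6.7 points of an arm's rate. Under the assumed 86% versus 71%, excluding failures shrinks the deficit to between 14.1 and 9.4 points, and free choice of visit raises the chance of NDGP looking equal or better from 21% to 30–34%. These sizes are illustrations; the conflict and the omissions can be read directly from the text.

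Two stronger inferences should be resisted. The text shows an open choice, with no evidence that anyone intends to use it. Nor is this a demonstrated inflation of type I error, since no clinical test is planned. The harm is a selected or attenuated success rate. The sponsor should correct this, but it is not a fatal flaw. It should be read with any separate point that the Statistical Analysis section contains no clinical analysis.

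**What to change.** For the analysis only, and before outcome data are analysed:

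1. **Extractions.** Reconcile the opening paragraph with the extraction paragraph so that an extraction for an endodontic reason counts as a failure even without periapical information. Add a sensitivity analysis that excludes those teeth.
2. **Primary outcome.** Name the strict definition at one stated visit. One year is the natural choice as the last planned visit, but fixing either in advance closes the gap. Report the other visit, the looser version (with 'and/or' changed to 'and') and tooth survival as labelled secondary outcomes.
3. **Retreated teeth.** Count a tooth that has had a secondary RCT before the deciding visit as a failure of the primary RCT, and report the number per arm.

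The cost is protocol wording and a little extra analysis, with no new visits or data. The reported success rate may be slightly lower, and a 1-year outcome will have more missing teeth than a 6-month one.
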